Upon enrollment, each patient will be randomly assigned to group A or group B. Patients in group A will be treated with TEA at ST36 and PC6 for 4 weeks, followed with a 2-week washout period and another 4-week period with sham TEA. Patients in group B will be treated with TEA and sham-TEA in a reversed order. The previous preliminary studies with EA or TEA were of duration of 2 weeks. To ensure better performance, we choose a treatment period of 4 weeks. A previous study has indicated that a washout period of 2 weeks is sufficient. The patients will not be informed of the exact locations of ST36 or PC6 and will not be informed that TEA at the sham points may be ineffective. The patients will be asked to come to the hospital 4 times: before the study (V1), end of the first 4 weeks (V2), end of washout period or beginning of the second 4-weeks (V3) and end of the second 4 weeks (V4). TEA or sham TEA will be performed three times daily, each initiated immediately after a meal and lasts for 2 hours. Various tests will be performed during each visit (see Fig.1 and Table 1). Symptoms of gastroparesis, assessment of constipation and questionnaire of quality of life (SF-36) as well as

TEA usage questionnaire will be completed during each of the 4 visits. The questionnaires will also be completed by the patient at home at the end of each week including the washout period.

The procedure for each visit is as follows: In the morning, GI symptom questionnaire, TEA use and SF-36 will be completed; then chest and abdominal surface electrodes will be placed and the noninvasive measurements of electrogastrogram (EGG) will be recorded for 2 hours. One hour after the recording, a test meal will be consumed by the subject and the recording will be continued for one more hour. Blood samples will be taken to measure gastrointestinal hormones such as NPY, ghrelin, CCK, motilin and VIP at different time points: at the initiation of the baseline recording of the EGG, immediately before the ingestion of the meal, 30 and 60min after the test meal. TEA or sham-TEA (according to the preceding treatment regime) will be performed during the tests for visits 2 and 4. No TEA or sham-TEA will be performed during visits 1 and 3 as these tests will be considered as baseline or control tests. For the patients with chronic constipation, no nutrient drink test will be conducted, symptoms related to constipation will be assessed, EGG will be recorded and blood samples will be collected.

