[figure not shown]

Table 1: Measurements during each of the scheduled visits (For patients with FD or Gastroparesis)

Time	GI Symptom Questionnaire	TEA Use	SF-36	EGG	Blood
Week 0 (V1)	+		+	+	+
Week 1	+	+			
Week 2	+	+			
Week 3	+	+			
Week 4 (V2)	+	+	+	+	+
Week 6 (V3)	+		+	+	+
Week 7	+	+			
Week 8	+	+			
Week 9	+	+			
Week10 (V4)	+	+	+	+	+

Notes:

- Abbreviations: V: visit; EGG: electrogastrogram.
- TEA Use questionnaires will be administered by telephone during weeks 1-3 and 7-9.

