#### **Assessment of gastroparesic symptoms, quality of life and use of TEA**

Dyspeptic and gastroparesic symptom questionnaire will use the previously validated gastroparesis cardinal symptom index (17), including 9 symptoms: nausea (feeling sick to your stomach as if you were going to vomit or throw up), retching (heaving as if to vomit, but nothing comes up), vomiting, stomach fullness, not able to finish a normal sized meal, feeling excessively full after meals, loss of appetite, bloating (feeling like you need to loose your clothes) and stomach or belly visibly larger. Each symptom will be graded from 0 to 5 (none, very mild, mild, moderate, severe and very severe).

Quality of life questionnaire Health-related QOL (HR-QOL, or QOL) symptom assessment will be performed using the validated SF-36 health form questionnaire with its specific scoring system.

Fig.2: The micro-stimulator (watch-like) to be used for TEA.

TEA use questionnaire 1) How many meals did you eat in the last 7 days? 2) How many of these meals did you apply the TEA? 3) When you use the TEA, about how long do you wear the stimulators?

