### **b. Study duration and number of study visits required of research participants.**

The study duration will be for 10 weeks, each patient will have 4 visits.

c. Blinding, including justification for blinding or not blinding the trial, if applicable.

Blinding of investigator is not practical as the investigator will be performing the procedure such as locate acupoints or sham-acupoints. However, the patients will be blinded to the TEA/sham TEA treatment.

d. Justification of why participants will not receive routine care or will have current therapy stopped.

Not Applicable.

e. Justification for inclusion of a placebo or non-treatment group.

Not Applicable. All the patients will have TEA treatment.

f. Definition of treatment failure or participant removal criteria.

Treatment failure will be defined as a lack of improvement in symptoms pre and post TEA treatment based on validated questionnaires and gastric motility assessment 6 and 12 months after the last treatment. Participant removal criteria will include any patient with moderate to severe adverse reaction to TEA or inability to tolerate the TEA conforming to standards of usual routine care.

g. Description of what happens to participants receiving therapy when study ends or if a participant's participation in the study ends prematurely.

The participant will follow up with their referring gastroenterologist and continued therapy will be left to the discretion of their provider.

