### b. Secondary outcome variables.

The secondary outcome measure of the study will include:

1. TEA use questionnaire.

2. Monthly assessment of quality of life questionnaire.

3. Autonomic functions,

4. GI hormones.

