### c. Statistical plan including sample size justification and interim data analysis.

Analysis of the outcomes will use a repeated measures regression model including fixed effects for treatment, patient and time period. The model will be estimated using 8 weekly observations (weeks 1-4 and 7-10) on percentage changes in symptoms score from baseline visit (V0) levels for each subject. Results will be expressed as least squares means for the percentage change in symptoms score observe under each treatment, and statistical significance of any difference between these means will be determined with a model-based t-test. A weekly estimate of percentage compliance with the prescribed TEA-use regimen based on patient response to the TEA-use questionnaire will be included in the estimated model as a covariate to address possible confounding of treatment and compliance effects.

In the current protocol, 40 FD patients, 40 gastroparesis patients and 40 constipation patients will be enrolled. The accuracy of the planned patients sample in each disease was assessed by Monte Carlo stimulation. Each simulated sample assumed the percentage change in symptom score outcome is normally distributed with a standard deviation of 38 and a correlation of 0.4 across repeated observations on the same subject. This parameterization was based on previous data from a similar cross-over study by Liu et al. comparing the effects active and sham TEA administered with a conventional TENS device on changes in the same gastrointestinal symptom score in functional dyspeptic patients (14). Results of the power simulation indicate that with complete follow-up the planned sample provides an 80% chance of detecting a cross-treatment difference in symptom score change equal to 10-11 percentage points with a two-sided significance level of 0.05. Even if 40% of follow-up data are missing at random due to drop-outs or missed follow-up contacts, the simulation results indicate the planned experiment would still have an 80% chance of detecting a cross-treatment difference in symptom score change of 13-14 percentage points with a two-sided significance level of 0.05.

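### The only planned efficacy model adjusts for weekly self-reported device use, which is measured after randomisation, so its TEA-versus-sham estimate is not the as-randomised comparison and can be biased in either direction

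*Combined protocol and SAP*

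**What the plan says.** Section 7c gives a single efficacy model: "Analysis of the outcomes will use a repeated measures regression model including fixed effects for treatment, patient and time period". It is fitted to eight weekly observations of percentage change in symptom score, and the least squares means and model-based t-test come from it. The section then adds a covariate: "A weekly estimate of percentage compliance with the prescribed TEA-use regimen based on patient response to the TEA-use questionnaire". No model without this covariate, no statement of analysis by assigned treatment and no sensitivity analysis appears in the document. The purpose given for the adjustment is that compliance "will be included in the estimated model as a covariate to address possible confounding of treatment and compliance effects".

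Patients are randomised to a treatment order at enrolment (section 4a), so every compliance value comes after randomisation. Table 1 collects device use in the same weeks as the symptom questionnaire, and its note reads "TEA Use questionnaires will be administered by telephone during weeks 1-3 and 7-9". The information is patient recall, for example "How many of these meals did you apply the TEA". Section 7b also lists the "TEA use questionnaire" first among the secondary outcomes.

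**The concern.** A confounder of the treatment comparison must influence which treatment is given. Here the order is randomised, and device use is observed afterwards, so it cannot play that part. The covariate instead conditions the efficacy estimate on another outcome of the trial. Bias follows if both of these hold:

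- **(a)** compliance is related to symptoms, given treatment;
- **(b)** compliance differs between TEA and sham, either directly or because an effective treatment changes use.

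If either fails, there is no bias. For FD and gastroparesis, (a) is plausible because use is tied to meals ("TEA or sham TEA will be performed three times daily, each initiated immediately after a meal and lasts for 2 hours") and the symptom index scores appetite and meal completion. That argument does not reach the constipation cohort, whose outcomes are bowel movements and PAC-SYM. On (b), equal use is likely to be helped by patient blinding but is not assured: section 4c states "Blinding of investigator is not practical as the investigator will be performing the procedure".

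Depending on signs, adjustment can shrink a real effect, inflate it, or create a difference where there is none. With no unadjusted result planned, a reader could not tell which had happened.

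**Working it through.** **Inputs from section 7c.** 40 patients per disease, 8 weekly observations (4 per treatment), SD 38, correlation 0.4, two-sided 0.05. Within-patient variance: v = (1 − 0.4) × 38² = 866.4.

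**The plan's own figure.** Without compliance, SE = √(2 × 866.4 / (4 × 40)) = 3.29. The difference detectable with 80% power is (1.96 + 0.84) × 3.29 ≈ 9.2 points, and power at 10, 10.5 and 11 points is 86%, 89% and 92%. The plan states 80% power at 10–11 points, which these inputs do not reproduce at 40 patients (about 30 patients would fit). With 40% missing, the detectable difference is 11.9 points in closed form, or 12.5–13 by simulation with random missingness, against the stated 13–14. The mismatch is conservative and is a separate matter. What counts here is that the model without compliance meets the stated power.

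**Effect of adjustment when symptoms move compliance.** Let Y be symptom improvement (positive = TEA better), T = 1 for TEA, d the true effect, and compliance C = 75 + aT + gY + noise with SD s. The values of a, g, s and the mean of 75 are assumptions; the documents give no compliance data. Within patient and treatment, the slope of Y on C is

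b = g·v / (g²·v + s²).

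Treatment shifts C by a + g·d, so

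adjusted estimate = d − b(a + g·d).

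For g = 0.2 and s = 15: b = 173.3 / (34.7 + 225) = 0.667. With d = 0 and a = 5 this gives −0.667 × 5 = −3.34. With d = 10 and a = 5 it gives 10 − 0.667 × 7 = 5.33.

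Simulation (3,000 runs per row; patient, treatment and period fixed effects plus compliance; s = 15):

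| d | a | g | Closed form | Simulated | Rejections |
|---|---|---|---|---|---|
| 0 | 0 | 0.2 | 0 | 0.05 | 5.3% |
| 0 | 5 | 0 | 0 | −0.07 | 5.0% |
| 0 | 1 | 0.2 | −0.67 | −0.63 | 5.4% |
| 0 | 2 | 0.2 | −1.33 | −1.33 | 7.5% |
| 0 | 5 | 0.2 | −3.34 | −3.35 | 19.2% |
| 0 | 5 | −0.2 | 3.34 | 3.32 | 18.9% |
| 0 | 10 | 0.2 | −6.67 | −6.70 | 53.9% |
| 10 | 0 | 0.1 | 9.63 | 9.64 | 83.9% |
| 10 | 0 | 0.2 | 8.67 | 8.67 | 80.1% |
| 10 | 0 | 0.3 | 7.43 | 7.37 | 72.2% |
| 10 | 5 | 0.2 | 5.33 | 5.42 | 40.6% |
| 10 | 5 | −0.2 | 12.00 | 12.01 | 97.3% |

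Without the covariate, rejection at d = 0 stays between 4.3% and 6.0%, and power at d = 10 is about 86%. The result is sensitive to s: with d = 0, a = 5 and g = 0.2, the size of the bias is 1.3 points (6.7% rejections) at s = 25 and 6.4 points (59.9%) at s = 10.

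**A second mechanism.** Assume compliance SD 15 and an unmeasured week-level factor correlated 0.5 with the symptom residual and ±0.6 with compliance. With no true effect, usage gaps of 5, 10 and 15 points give biases of about 2.9, 5.9 and 8.8 points, with about 15%, 43% and 69% false rejections. With no gap there is no bias.

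**If use itself affects symptoms**, which seems to be the plan's premise, and use is equal, both models are unbiased. With a 5-point gap and 0.5 points of symptom change per point of use, a total effect of 10 is 7.5 direct plus 0.5 × 5 = 2.5 through use. The adjusted model reports only the direct part (7.56 simulated; power 64.8% against 86.1% unadjusted).

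**The case against.** The strongest reply is that the documents lean against a usage gap. Patients are blinded, are not told that sham points may be ineffective, receive the same stimulator output, and are excluded if they have had acupuncture or know the points. No mechanism is given from an unblinded investigator to unequal use at home. Who is unblinded is itself unclear: section 4a calls the design double-blinded and refers to an unblinded programmer. With gaps of 1–2 points and no true effect, rejection is 5.4–7.5%, close to nominal.

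The meal argument also depends on the denominator. If compliance is treated meals over meals eaten, a skipped meal leaves both counts and poor appetite does not mechanically lower it. If the denominator is the three-times-daily regimen, it does. Section 7c does not settle which.

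The larger illustrative figures need strong inputs. A slope of 0.2 with noise SD 15 implies a within-patient compliance-symptom correlation of about 0.37, and the most extreme rows about 0.51. Simulated compliance has no ceiling, so about 7% of values exceed 100% at g = 0.2 and s = 15. Patient fixed effects do remove stable differences between patients.

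All of this stands as a limit on size: the bias may be small. None of it supplies a reason for the covariate. Patient effects do not remove week-to-week links, and a treatment that works can shift use even when there is no direct gap.

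**Conclusion.** The point holds. The planned efficacy test conditions on a post-randomisation outcome, the reason given is not valid in a randomised comparison, and the as-randomised estimate is not planned at all. This follows from the text and needs no assumption. It affects the efficacy test in all three cohorts, although the meal-based argument for a compliance-symptom link applies only to FD and gastroparesis.

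The size is not known. It rests on assumed usage gaps, slopes and noise, and ranges from nothing, when either condition fails, to several points on a scale where the trial is built to detect 10–11. The direction may favour TEA or sham. The matter should be corrected before analysis.

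**What to change.** In section 7c, state that the primary analysis is the model with treatment, period and patient only, by assigned treatment, without the compliance covariate. Report compliance by treatment as the secondary outcome it already is. Keep any compliance-adjusted model as a labelled exploratory analysis.

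This takes one sentence and no new data. The downside is some loss of precision if use truly affects symptoms and is equal under TEA and sham. With assumed effects of 0.2, 0.5 or 1.0 points of symptom change per point of use (total SD held at 38, true effect 10, 5,000 runs), power without and with the covariate is 85.2% and 85.4%, 86.0% and 87.8%, or 86.7% and 94.5%.

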### **Assessment of symptoms for patients with chronic constipation**

Symptoms: 1) Number of spontaneous complete bowel movement (SCBM) per week. 2) Patient Assessment of Constipation Symptoms (PAC-SYM). Stool diary during the entire experimental period to assess bowel movement, including number and time of defecation, stool quality, straining and medications or any other methods used for defecation; stool consistency will be assessed according to the Bristol Stool Form Scale. PAC-SYM questionnaire will be completed every two weeks. 3) Quality of life (PAC-QoL): the questionnaires will be completed at all visits.

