## 7. Study Statistics

### a. Primary outcome variable.

The primary outcome of this study is GI symptoms including weekly GI symptom questionnaire; number of spontaneous complete bowel movement (SCBM) per week; and Patient Assessment of Constipation Symptoms (PAC-SYM), once every two weeks.

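### The 80% power figure given for each disease rests on dyspepsia-score variability and eight weekly values, so it is not supported for the constipation cohort's primary outcomes (weekly SCBM, two-weekly PAC-SYM)

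*Combined protocol and SAP*

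**What the plan says.** Section 7c plans that "40 FD patients, 40 gastroparesis patients and 40 constipation patients will be enrolled" and continues: "The accuracy of the planned patients sample in each disease was assessed by Monte Carlo stimulation". One set of simulation inputs is given: percentage change in symptom score, "normally distributed with a standard deviation of 38 and a correlation of 0.4 across repeated observations on the same subject". The source is an earlier crossover study of active and sham TEA on "changes in the same gastrointestinal symptom score in functional dyspeptic patients". The model uses eight weekly values per patient (weeks 1-4 and 7-10) with fixed effects for treatment, patient and period. The result is 80% power at 10-11 points with complete follow-up and at 13-14 points with 40% missing, two-sided 0.05.

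Section 7a lists three primary outcomes: the weekly GI symptom questionnaire, "number of spontaneous complete bowel movement (SCBM) per week", and PAC-SYM once every two weeks. Section 4a (assessment of symptoms for patients with chronic constipation) assigns SCBM and PAC-SYM to the constipation cohort, and PAC-SYM is again two-weekly there. No rate, SD, correlation, target effect or power figure is given for either.

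**The concern.** The power statement covers three cohorts, but its inputs describe one instrument in one disease. The constipation cohort differs in two ways that affect precision.

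- SCBM per week is a count. As a percentage of a low baseline rate, it may vary far more from week to week than a multi-item score does.
- PAC-SYM supplies two values per four-week period, not the four that the model assumes.

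As 7c stands, a reader would take 40 constipation patients as enough to detect 10-11 points on that cohort's primary outcomes. Someone interpreting a non-significant result would have no sound figure for what the cohort could have detected.

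**Working it through.** **Inputs from the documents.** N = 40 per disease; two-period crossover ("each patient will be randomly assigned to group A or group B"; equal allocation assumed, as the ratio is not stated); four weekly values per treatment; SD 38; correlation 0.4, read as equal between all pairs of weeks; two-sided 0.05.

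**Formulas.** Patient effects remove between-patient variation. With within-patient variance v and m values per period, SE(TEA minus sham) = √(2v/(m × 40)). The 80%-power difference is (1.96 + 0.84) × SE = 2.80 × SE. Powers below use the t distribution with the model's residual df: 320 − 42 = 278 for weekly data, 160 − 42 = 118 for two-weekly data.

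**Step 1: the plan's own figure.** v = 38² × (1 − 0.4) = 866.4, a within-patient SD of 29.4. SE = √(2 × 866.4/160) = 3.29, so the detectable difference is 9.2 points and power is 86% at 10 and 91% at 11. Simulation of the planned model agrees (86% and 91%). With 40% missing, simulated power is 81% at 13 and 88% at 14. For the score it describes, the stated figure is therefore slightly conservative.

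**Step 2: SCBM.** The documents give no baseline rate or variance, so both are assumed: rate B of 1, 2 or 3 per week, and variance equal to φ times the Poisson variance. With B known, percentage change has weekly variance v = 10,000φ/B.

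| φ | B per week | SE | Power at 10-11 points | 80%-power difference |
|---|---|---|---|---|
| 1 (Poisson) | 1 | 11.18 | 14-16% | 31.3 points |
| 1 | 2 | 7.91 | 24-28% | 22.1 |
| 1 | 3 | 6.45 | 34-40% | 18.1 |
| 0.5 | 1 | 7.91 | 24-28% | 22.1 |
| 0.5 | 2 | 5.59 | 43-50% | 15.7 |
| 0.5 | 3 | 4.56 | 59-67% | 12.8 |
| 0.25 | 1 | 5.59 | 43-50% | 15.7 |
| 0.25 | 2 | 3.95 | 71-79% | 11.1 |
| 0.25 | 3 | 3.23 | 87-92% | 9.0 |

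Simulated Poisson counts with a known baseline gave 14%, 25% and 35% at 10.5 points for B = 1, 2 and 3. Poisson noise, 100/√B, falls to the plan's within-patient 29.4 only at B = 10,000/866.4 = 11.5 per week.

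In SCBM per week, the Poisson detectable differences are 0.313 × 1 = 0.31, 0.221 × 2 = 0.44 and 0.181 × 3 = 0.54.

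A known baseline is favourable. With one observed Poisson baseline week, simulated power at 10.5 points was 9%, 20% and 26%. About 37%, 14% and 5% of patients (e^−B) would have a zero baseline and so no defined percentage change.

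**Step 3: PAC-SYM.** Keep SD 38 and correlation 0.4, with m = 2. SE = √(2 × 866.4/80) = 4.65. Power is 57% at 10 and 65% at 11; the detectable difference is 2.80 × 4.65 = 13.0 points. This step changes only the number of values per period.

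**The case against.** **The stated figure is about a symptom score.** Section 7c words both power statements as symptom score change, and SCBM is not a score. A reader might infer that the plan makes a false 80% claim for SCBM by name; it does not. That stands. The claim reaches constipation only because the sample in each disease is said to have been assessed. If the figure was never meant for SCBM, then SCBM has no sample size justification and the same edit is needed. If it was meant for PAC-SYM, step 3 applies.

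**The SCBM result is conditional.** A reader might infer that count noise must exceed an SD of 38 and that SCBM power is certainly far below 80%. The documents do not support that: they give no rate or distribution. At a quarter of the Poisson variance the claim is met from about 3 per week. At half the Poisson variance it would be met at 5 per week, where v = 1,000, SE = 3.54 and the detectable difference is 9.9 points.

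**No calculation in 7c is shown to be wrong.** This also stands. Step 1 shows the figure to be conservative for its own inputs; the fault lies in where it is applied.

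**Nothing makes 10 points the SCBM target.** True. Detecting 0.31-0.54 SCBM per week may be adequate, and this review does not show that a relevant effect would be missed. The plan should state the figure so that a reader can judge.

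**Conclusion.** The concern holds as a missing justification. The 10-11 and 13-14 point figures are not supported for either constipation primary outcome, because their inputs come from a dyspepsia score in FD patients observed weekly. That much follows from the documents alone.

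The size rests on assumptions. For SCBM at an assumed 1-3 per week with a known baseline rate, power at 10-11 points is about 14-40% if counts are Poisson, 24-67% at half that variance and 43-92% at a quarter. For PAC-SYM, the plan's own SD and correlation, themselves an assumption for that instrument, give about 57-65% and a detectable difference of about 13 points.

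It would go too far to say that the plan misstates SCBM power by name, that SCBM power is known to be low, or that 7c contains an arithmetic error.

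**What to change.** In section 7c:

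- Limit the 10-11 and 13-14 point statements to the nine-item symptom score. Note that the SD of 38 comes from FD patients and is an assumption for the gastroparesis cohort.
- For SCBM, state a detectable difference at N = 40 in SCBM per week over a stated range of assumed rates and variances. If Poisson, this is about 0.31, 0.44 and 0.54 per week at 1, 2 and 3 per week.
- For PAC-SYM, state a detectable difference at N = 40 based on two values per period: about 13 points if SD 38 and correlation 0.4 are assumed.

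This costs wording and a short calculation, with no extra patients. The downside is a less favourable stated figure for the constipation cohort.
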